6.0 TRIAL FLOW CHART FIRST COURSE OF TREATMENT

Trial Period:			Treatr	nent C	ycles					End of Treatment		Post-Treatment	
	Screening	1			4	To b		ted bey cles	ond 8		Safety		Surviva
Treatment Cycle/Title:			2	3		5	6	7	8	Discon	Follow- up	Follow Up Visits	Follow- Up
Scheduling Window (Days):	-28 to 1		± 3	± 3	± 3	± 3	± 3	± 3	± 3	At time of Discon	30 days post discon	Every 8 weeks post discon	Every 12 weeks
Informed Consent	Х												
Inclusion/Exclusion Criteria	Х												
Demographics and Medical History	Х												
Trial Treatment Administration		Х	Х	Х	Х	Х	Х	Х	Х				
Survival Status													Х
Review Adverse Events		Х	Х	Х	Х	Х	Х	Х	Х	Х	Х		
Full Physical Examination	Х												
Directed Physical Examination		Х	Х	Х	Х	Х	Х	Х	Х	Х	Х		
Vital Signs and Weight	Х	Х	Х	Х	Х	Х	Х	Х	Х	Х			
ECOG Performance Status	Х	Х	Х	Х	Х	Х	Х	Х	Х	Х			
Pregnancy Test – Urine or Serum β -HCG	X ^a												
PT/INR and aPTT	Х												
CBC	Х	Х	Х	Х	Х	Х	Х	Х	Х	Х	Х		
Comprehensive Serum Chemistry Panel (see 7.1.3.1)	Х	Х	X	X	X	X	X	Х	X	Х	Х		
Urinalysis	Х												
T3, FT4 and TSH	Х												
Tumor Imaging (see section 7.1.2.6)	Х				Х		Х						
Archival or Newly Obtained Tissue Collection (see section 7.1.2.7)	Х				Х								

Trial Period:		Treatment Cycles						End of Treatment		Post-Treatment			
	Screening	1			4	To b	~	ted beyo cles	ond 8	Safety		5	
Treatment Cycle/Title:			2	3		5	6	7	8	Discon	Follow- up	Follow Up Visits	Follow- Up
Scheduling Window (Days):	-28 to 1		± 3	± 3	± 3	± 3	± 3	± 3	± 3	At time of Discon	30 days post discon	Every 8 weeks post discon	Every 12 weeks
Correlative Studies Blood Collection (see section 7.1.2.7)	Х				Х					Х			

Confidential 📀 Limited Access

6.1 TRIAL FLOW CHART SECOND COURSE OF TREATMENT

Trial Period:	Treatment Cycles						End of Treatment		Post-Treatment				
	Screening	1			4	To b		ted bey cles	ond 8		Safety		Surviva 1
Treatment Cycle/Title:			2	3		5	6	7	8	Discon	Follow- up	Follow Up Visits	Follow- Up
Scheduling Window (Days):	-28 to 1		± 3	± 3	± 3	± 3	± 3	± 3	± 3	At time of Discon	30 days post discon	Every 8 weeks post discon	Every 12 weeks
Inclusion/Exclusion Criteria (See Section 5.1.4)	Х												
Trial Treatment Administration		Х	Х	Х	Х	Х	Х	Х	Х				
Survival Status													Х
Review Adverse Events		Х	Х	Х	Х	Х	Х	Х	Х	Х	Х		
Full Physical Examination	Х												
Directed Physical Examination		Х	Х	Х	Х	Х	Х	Х	Х	Х	Х		
Vital Signs and Weight	Х	Х	Х	Х	Х	Х	Х	Х	Х	Х			
ECOG Performance Status	Х	Х	Х	Х	Х	Х	Х	Х	Х	Х			
Pregnancy Test – Urine or Serum β -HCG	Х												
PT/INR and aPTT	Х												
CBC	Х	Х	Х	Х	Х	Х	Х	Х	Х	Х	Х		
Comprehensive Serum Chemistry Panel (see 7.1.3.1)	Х	Х	Х	X	Х	X	Х	Х	Х	Х	Х		
Urinalysis	Х												
T3, FT4 and TSH	Х												
Tumor Imaging (see section 7.1.2.6)	Х				Х		Х						
Archival or Newly Obtained Tissue Collection (see section 7.1.2.7)	Х				Х								
Correlative Studies Blood Collection (see section 7.1.2.7)	Х				Х					Х			

39

7.0 TRIAL PROCEDURES

7.1 Trial Procedures

The Trial Flow Chart - Section 6.0 summarizes the trial procedures to be performed at each visit. Individual trial procedures are described in detail below. It may be necessary to perform these procedures at unscheduled time points if deemed clinically necessary by the investigator.

Furthermore, additional evaluations/testing may be deemed necessary by the Sponsor and/or Merck for reasons related to subject safety. In some cases, such evaluation/testing may be potentially sensitive in nature (e.g., HIV, Hepatitis C, etc.), and thus local regulations may require that additional informed consent be obtained from the subject. In these cases, such evaluations/testing will be performed in accordance with those regulations.

7.1.1 Administrative Procedures

7.1.1.1 Informed Consent

The Investigator must obtain documented consent from each potential subject prior to participating in a clinical trial.

7.1.1.1.1 General Informed Consent

Consent must be documented by the subject's dated signature or by the subject's legally acceptable representative's dated signature on a consent form along with the dated signature of the person conducting the consent discussion.

A copy of the signed and dated consent form should be given to the subject before participation in the trial.

The initial informed consent form, any subsequent revised written informed consent form and any written information provided to the subject must receive the IRB/ERC's approval/favorable opinion in advance of use. The subject or his/her legally acceptable representative should be informed in a timely manner if new information becomes available that may be relevant to the subject's willingness to continue participation in the trial. The communication of this information will be provided and documented via a revised consent form or addendum to the original consent form that captures the subject's dated signature or by the subject's legally acceptable representative's dated signature.

The informed consent will adhere to IRB/ERC requirements, applicable laws and regulations and Sponsor requirements.

7.1.1.2 Inclusion/Exclusion Criteria

All inclusion and exclusion criteria will be reviewed by the investigator or qualified designee to ensure that the subject qualifies for the trial.

7.1.1.3 Medical History

A medical history will be obtained by the investigator or qualified designee. Medical history will include all active conditions, and any condition diagnosed within the prior 10 years that are considered to be clinically significant by the Investigator. Details regarding the disease for which the subject has enrolled in this study will be recorded separately and not listed as medical history.

7.1.1.4 **Prior and Concomitant Medications Review**

7.1.1.4.1 Prior Medications

The investigator or qualified designee will review prior medication use, including any protocol-specified washout requirement, and record prior medication taken by the subject within 28 days before starting the trial. Treatment for the disease for which the subject has enrolled in this study will be recorded separately and not listed as a prior medication.

7.1.1.5 Disease Details and Treatments

7.1.1.5.1 Disease Details

The investigator or qualified designee will obtain prior and current details regarding disease status.

7.1.1.5.2 **Prior Treatment Details**

The investigator or qualified designee will review all prior cancer treatments including systemic treatments, radiation and surgeries.

7.1.1.5.3 Subsequent Anti-Cancer Therapy Status

The investigator or qualified designee will review all new anti-neoplastic therapy initiated after the last dose of trial treatment. If a subject initiates a new anti-cancer therapy within 30 days after the last dose of trial treatment, the 30 day Safety Follow-up visit must occur before the first dose of the new therapy. Once new anti-cancer therapy has been initiated the subject will move into survival follow-up.

7.1.1.6 Assignment of Screening Number

Patients will be assigned a screening number upon consent.

7.1.1.7 Assignment of Randomization Number

There is no randomization number.

7.1.2 Clinical Procedures/Assessments

7.1.2.1 Adverse Event (AE) Monitoring

The investigator or qualified designee will assess each subject to evaluate for potential new or worsening AEs as specified in the Trial Flow Chart and more frequently if clinically indicated. Adverse experiences will be graded and recorded throughout the study and during the follow-up period according to NCI CTCAE Version 4.0 (see Section 12.2). Toxicities will be characterized in terms regarding seriousness, causality, toxicity grading, and action taken with regard to trial treatment.

All AEs of unknown etiology associated with MK-3475 exposure should be evaluated to determine if it is possibly an event of clinical interest (ECI) of a potentially immunologic etiology (irAE). See Section 5.6.1.1 and the separate guidance document in the administrative binder regarding the identification, evaluation and management of AEs of a potential immunological etiology.

Please refer to section 7.2 for detailed information regarding the assessment and recording of AEs.

7.1.2.2 Full Physical Exam

The investigator or qualified designee will perform a complete physical exam during the screening period. Clinically significant abnormal findings should be recorded as medical history. A full physical exam should be performed during screening,

7.1.2.3 Directed Physical Exam

For cycles that do not require a full physical exam per the Trial Flow Chart, the investigator or qualified designee will perform a directed physical exam as clinically indicated prior to trial treatment administration.

7.1.2.4 Vital Signs

The investigator or qualified designee will take vital signs at screening, prior to the administration of each dose of trial treatment and at treatment discontinuation as specified in the Trial Flow Chart (Section 6.0). Vital signs should include temperature, pulse, respiratory rate, weight and blood pressure.

7.1.2.5 Eastern Cooperative Oncology Group (ECOG) Performance Scale

The investigator or qualified designee will assess ECOG status (see Section 12.4) at screening, prior to the administration of each dose of trial treatment and discontinuation of trial treatment as specified in the Trial Flow Chart.

7.1.2.6 Tumor Imaging and Assessment of Disease

Radiologic assessments of measurable disease will be performed using contrast CT imaging. RECIST 1.1 and IrRC criteria will be used to assess response to therapy. Radiologic imaging will be performed every 9 weeks ($63 \pm 7 days$). After completion of cycle #6, the intervals between radiographic evaluations can be extended to up to 12 weeks $\pm 7 days$, according to the discretion of the treating physician.

Radiographic imaging (RECIST 1.1 and IrRC) will be completed at a minimum of 9 weeks (63 +/- 7 days) of starting the MK-3475 and vorinostat combination. Patients who have objective responses or stable disease will continue therapy. Patients who obtain clinical benefit from the combination will be allowed to continue therapy for a maximum of 2 years, or until progression or severe toxicity, whichever comes first.

Patients can be treated for a maximum of 2 cycles before a confirmatory scan for a CR is performed.

Patients who do not achieve a RECIST 1.1 criteria objective response at the first radiographic evaluation can continue the combination of vorinostat and MK-347 provided that they do not demonstrate clinical deterioration (defined by the following parameters and determined by the treating physician):

- 1. Absence of signs and symptoms of disease progression
- 2. No decline in ECOG performance status
- 3. Absence of rapid disease progression
- 4. Absence of progressive tumor at critical anatomical sites (e.g. cord compression) requiring urgent alternative medical intervention.

Patients who receive a confirmed CR on trial may consider discontinuation of treatment. Upon progression they can be retreated on a second course of therapy according to Table 2.1. patients who progress on the second course of therapy are off study.

7.1.2.7 Tumor Tissue Collection and Correlative Studies Blood Sampling

All patients will be required to submit archival tissue as part of study participation. In patients who do not have archival tissue, a pretreatment tumor biopsy will be performed, unless deemed contraindicated by the treating physician. Every attempt to obtain additional tumor biopsies will be performed after 3 cycles of treatment are completed. Similarly,

exceptions will be made for patients in whom the treating physician feels a repeat biopsy is contraindicated. These samples will be submitted centrally for immunohistochemical expression studies involving proteins in the PD-1 family as well as CD3, CD69 and FOXP3.

Research blood collections will be obtained for correlative research studies on the following timepoints: Prior to initiation of therapy (day 1 cycle 1), and after 3 cycles of treatment, and at treatment discontinuation or progression. We intend to perform flow cytometric evaluation of CD3, CD4, CD8, CD14, PD-1, PD-L1, PD-L2 on peripheral blood mononuclear cells.

Specimen Requirements: Submission for flow cytometry

• A 5-10 mL specimen of peripheral blood in a lavender- (EDTA) or green- (sodium heparin) tube is acceptable for each draw.

• Storage/Transport Temperature: Specimens can be transported with a cold pack or wet ice, but do not fix or freeze specimens.

• Unacceptable Conditions: Frozen specimens, specimens greater than 48 hours old, specimens fixed in formalin for flow cytometry

• Address for shipping specimens:

Attn: [name], Hematopathology Lead

Seattle Cancer Care Alliance

Hematopathology Laboratory G7800

[name]

[name]

7.1.3 Laboratory Procedures/Assessments

Details regarding specific laboratory procedures/assessments to be performed in this trial are provided below.

7.1.3.1 Laboratory Safety Evaluations (Hematology, Chemistry and Urinalysis)

Laboratory tests for hematology, chemistry, urinalysis, and others are specified in Table 9.

Product: MK-3475 **Protocol/Amendment No.:**

Table 9 Laboratory Tests

Hematology	Chemistry	Urinalysis	Other
Hematocrit	Albumin	Blood	Serum β-human chorionic gonadotropin†
Hemoglobin	Alkaline phosphatase	Glucose	(β-hCG)†
Platelet count	Alanine aminotransferase (ALT)	Protein	PT (INR)
WBC (total)	Aspartate aminotransferase (AST)	Specific gravity	aPTT
Red Blood Cell Count	Lactate dehydrogenase (LDH)	Microscopic exam (If abnormal)	Total thriiodothyronine (T3)
Absolute Neutrophil Count	Carbon Dioxide ‡	results are noted	Free thyroxine (T4)
	$(CO_2 \text{ or bicarbonate})$	Urine pregnancy test †	Thyroid stimulating hormone (TSH)
	Calcium		
	Chloride		Blood for correlative studies
	Glucose		
	Potassium		
	Sodium		
	Total Bilirubin		
	Direct Bilirubin (If total bilirubin is elevated above the upper limit of normal)		
	Total protein		
	Blood Urea Nitrogen		

Laboratory tests for screening or entry into the Second Course Phase should be performed within 10 days prior to the first dose of treatment. After Cycle 1, pre-dose laboratory procedures can be conducted up to 72 hours prior to dosing. Results must be reviewed by the investigator or qualified designee and found to be acceptable prior to each dose of trial treatment.

7.1.4 Other Procedures

7.1.4.1 Withdrawal/Discontinuation

When a subject discontinues/withdraws prior to trial completion, all applicable activities scheduled for the final trial visit should be performed at the time of discontinuation. Any adverse events which are present at the time of discontinuation/withdrawal should be followed in accordance with the safety requirements outlined in Section 7.2 - Assessing and Recording Adverse Events. Subjects who a) attain a CR or b) complete 24 months of treatment with MK-3475 may discontinue treatment with the option of restarting treatment if they meet the criteria specified in Section 7.1.5.2.1. After discontinuing treatment following assessment of CR, these subjects should return to the site for a Safety Follow-up Visit (described in Section 7.1.5.3.1) and then proceed to the Follow-Up Period of the study (described in Section 7.1.5.4).

7.1.5 Visit Requirements

Visit requirements are outlined in Section 6.0 - Trial Flow Chart. Specific procedure-related details are provided above in Section 7.1 - Trial Procedures.

7.1.5.1 Screening Period

The following assessments will be performed up to 28 days prior to initiation of study treatment:

- 1. Full Physical Examination
- 2. Vital Signs and weight
- 3. Pregnancy test or Serum B-HCG in females of childbearing age (within 72 hours of starting therapy)
- 4. CBC (within 10 days of starting therapy)
- 5. PT/INR and aPTT (within 10 days of starting therapy)
- 6. Comprehensive Serum Chemistry panel (within 10 days of starting therapy)
- 7. Urinalysis (within 10 days of starting therapy)
- 8. T3, FT4 and TSH (within 10 days of starting therapy)
- 9. Tumor imaging of known sites of disease

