7.1.5.2 Treatment Period

The following assessments will be performed on day 1 of each cycle and must be performed no more than 24 hours prior to treatment unless otherwise specified. The only exception is for day 1 when the assessments will serve as baseline assessments and can be performed up to 3 weeks prior or as otherwise specified.

- 1. Adverse event review
- 3. Directed physical examination
- 4. Vital signs and weight
- 5. ECOG performance status
- 5. CBC
- 6. Comprehensive serum chemistry panel
- 6. Tumor Assessments of known sites of disease (every 9 weeks; 63 +/- 7 days)

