7.2.3.2 Events of Clinical Interest

Selected non-serious and serious adverse events are also known as Events of Clinical Interest (ECI) and must be recorded as such on the Adverse Event case report forms/worksheets and reported within 24 hours to the Sponsor and within 2 working days to Merck Global Safety. (Attn: Worldwide Product Safety; [contact])

Events of clinical interest for this trial include:

1. an overdose of Merck product, as defined in Section 7.2.1 - Definition of an Overdose for This Protocol and Reporting of Overdose to the Sponsor, that is not associated with clinical symptoms or abnormal laboratory results.

2. an elevated AST or ALT lab value that is greater than or equal to 3X the upper limit of normal and an elevated total bilirubin lab value that is greater than or equal to 2X the upper limit of normal and, at the same time, an alkaline phosphatase lab value that is less than 2X the upper limit of normal, as determined by way of protocol-specified laboratory testing or unscheduled laboratory testing.*

*Note: These criteria are based upon available regulatory guidance documents. The purpose of the criteria is to specify a threshold of abnormal hepatic tests that may require an additional evaluation for an underlying etiology. The trial site guidance for assessment and follow up of these criteria can be found in the Investigator Trial File Binder (or equivalent).

3. In the event a subject develops any of the following AEs, a detailed narrative of the event should be reported as an ECI to the Sponsor within 24 hours and to Merck Global Safety within 2 working days of the event:

- a. Grade \geq 3 diarrhea
- b. Grade \geq 3 colitis
- c. Grade ≥ 2 pneumonitis
- d. Grade \geq 3 hypo- or hyperthyroidism

A separate guidance document has been provided entitled "event of Clinical Interest and Immune-Related Adverse Event Guidance Document." This document provides guidance regarding identification, evaluation and management of ECIs and irAEs. Additional ECIs are identified in this guidance document and also need to be reported to the Sponsor within 24 hours and to Merck Global Safety within 2 working days of the event.

Subjects should be assessed for possible ECIs prior to each dose. Lab results should be evaluated and subjects should be asked for signs and symptoms suggestive of an immune-

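### T3, FT4 and TSH are scheduled only at screening, so the pre-dose review for events of clinical interest has no planned thyroid result after baseline

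*Combined protocol and SAP*

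**What the plan says.** Section 7.2.3.2 lists grade 3 or higher "hypo- or hyperthyroidism" among the ECIs to be reported to the Sponsor within 24 hours. It then directs: "Subjects should be assessed for possible ECIs prior to each dose. Lab results should be evaluated and subjects should be asked for signs and symptoms".

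The thyroid tests appear once per course. The screening list in 7.1.5.1 has "T3, FT4 and TSH (within 10 days of starting therapy". The first-course chart (6.0) has one mark, under Screening. The second-course chart (6.1) has one mark, at re-screening for retreatment.

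Section 7.1.5.2 opens with "The following assessments will be performed on day 1 of each cycle" and names CBC and the chemistry panel as the blood tests. It names no thyroid test. In Table 9 (7.1.3.1), "Thyroid stimulating hormone (TSH", T3 and free T4 stand in the column for other tests, not under Chemistry.

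On-treatment testing can arise in other ways. Section 7.1 allows unscheduled procedures when the investigator thinks them necessary. Section 7.1.2.1 states: "All AEs of unknown etiology associated with MK-3475 exposure should be evaluated to determine if it is possibly an event of clinical interest (ECI". Section 7.2.3.2 calls for further testing once labs or symptoms point to an immune-related ECI. None of these provisions names thyroid tests. A separate ECI guidance document is listed as Appendix 12.8 but is not reproduced.

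**The concern.** The protocol singles out a thyroid event for expedited reporting and sets a pre-dose review based partly on laboratory results. Its own schedule supplies no thyroid result to that review once treatment has begun. A site that followed the flow chart exactly would test thyroid function on treatment only when a symptom or a clinician's suspicion prompted it.

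Safety and tolerability is the primary objective. Fatigue is where a missed prompt is most plausible. Section 5.2.2 answers drug-related fatigue with bedtime vorinostat dosing, the toxicity table in 5.2.1.2 handles grade 2 fatigue like grade 1, and 5.2.1.2 admits that attributing toxicity to one agent is difficult. Patients with hypothyroidism stable on replacement may also enrol (5.1.3), and no scheduled test follows them on treatment.

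Detection below grade 3 has a defined use. Under 5.6.1.1, a grade 2 or higher immune-related event is to be discussed immediately with the Sponsor, and MK-3475 may be withheld at grade 2.

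**Working it through.** The plan states no figure on this point to reproduce. The check compares the schedules and then counts tests.

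**Schedule after baseline.** In 6.0, CBC and chemistry are marked at screening, every cycle, discontinuation and the 30-day visit. The thyroid row is marked at screening only. Scheduled thyroid panels after baseline in the first course: 0. The hepatic ECI in 7.2.3.2 makes a useful comparison. Its four components (AST, ALT, total bilirubin, alkaline phosphatase) are all in the chemistry panel and so are drawn every cycle.

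**Inputs for the counts.**
- Cycle length is 21 days, or 28 days in the fallback regimen (2.1.1).
- The maximum first course is 24 months, 730.5 days (5.8).
- The second course lasts up to one year, 365 days (2.1.2).
- Assumption: typical treatment lasts 5 to 6 months (152 to 183 days), the historical median PFS in salivary cancer quoted in 4.1.2. The documents give no PFS for the squamous cohort.
- The screening thyroid test may precede day 1 by up to 10 days (7.1.5.1).

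**Formulas.** Cycle starts = floor(days / cycle length) + 1. Panels under the example schedule = number of starts among cycles 4, 7, 10 and so on, plus 2 (discontinuation and 30-day visit).

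| Case | Cycle starts | On-treatment panels | Total added |
|---|---|---|---|
| 21-day, 5 months | floor(152/21)+1 = 8 | 2 (C4, C7) | 4 |
| 21-day, 6 months | floor(183/21)+1 = 9 | 2 (C4, C7) | 4 |
| 21-day, 24 months | floor(730.5/21)+1 = 35 | 11 (C4 to C34) | 13 |
| 21-day, one-year second course | floor(365/21)+1 = 18 | 5 (C4 to C16) | 7 |
| 28-day, 5 months | floor(152/28)+1 = 6 | 1 (C4) | 3 |
| 28-day, 6 months | floor(183/28)+1 = 7 | 2 (C4, C7) | 4 |
| 28-day, 24 months | floor(730.5/28)+1 = 27 | 8 (C4 to C25) | 10 |

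A patient who stops before cycle 4 has 0 + 2 = 2 panels. The 21-day maximum over both courses is 13 + 7 = 20.

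**Reviews without a fresh result.** Over 24 months there are up to 35 pre-dose reviews at 21 days, or 27 at 28 days. The screening panel serves the first, leaving up to 34 or 26 with no new scheduled thyroid result.

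**Draws already planned.** At 5 to 6 months on 21-day cycles there are 8 + 2 = 10 to 9 + 2 = 11 CBC and chemistry draws from cycle 1 through the 30-day visit. None includes thyroid tests.

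**Longest planned interval.** At present it is the whole course: about 152 to 183 days under the assumption, and up to about 730 days. Under the example schedule, successive on-treatment tests are 3 × 21 = 63 days apart (3 × 28 = 84). The first interval, from screening to cycle 4, is up to 10 + 63 = 73 days (10 + 84 = 94). These figures assume that cycles run on time and ignore the 3-day visit window. Dose delays would lengthen them.

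**The case against.** The strongest reply is that the documents do not establish a failure of monitoring. The protocol sends the identification and evaluation of immune-related events to the ECI guidance document, which is not available here and may call for periodic thyroid tests. That stands. The supported claim is limited to the flow charts and visit lists.

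A reader might also infer that 7.2.3.2 requires a thyroid test before each dose, so that the schedule contradicts it. It does not. The instruction is a general review of labs and symptoms. Diarrhea, colitis and pneumonitis are on the same ECI list without a dedicated scheduled lab.

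A further tempting inference is that severe thyroid events would be missed or the safety results biased. The documents do not support that either. Table 10 defines grade 3 in clinical terms, and each cycle has adverse event review, directed examination, vital signs and ECOG status, where most such cases should appear. Mild abnormalities need no action under Table 6 and are generally not recorded under 7.2, so added tests would not give an unbiased rate of all thyroid events.

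The fatigue argument is plausible rather than shown. The bedtime-dosing advice concerns fatigue already judged drug-related, and the grade 2 exception governs holding treatment, not diagnosis. Neither waives a work-up. What remains is that, within the visit schedule, on-treatment thyroid testing depends on someone suspecting a thyroid cause.

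**Conclusion.** The point holds as a low-cost improvement. Both flow charts and the visit lists schedule thyroid tests only at screening or re-screening, and the per-cycle chemistry panel does not contain them. No scheduled thyroid result after baseline therefore reaches the pre-dose ECI review.

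The expected gain is earlier detection below grade 3 and better attribution of fatigue-like symptoms. Its size is unknown because the documents give no thyroid event frequency. The DLT rule, response test, sample size and analysis are unaffected. The panel counts for a typical patient rest on the 5 to 6 month assumption, but the count of zero scheduled tests after baseline does not. Confidence is medium, because the guidance document could already cover the need. If it does, the flow charts should show it.

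**What to change.** Extend the T3/FT4/TSH row in 6.0 and 6.1, and add one line to 7.1.5.2, so that the tests are run on existing draws at a fixed interval, at discontinuation and at the 30-day safety visit. Every 3 cycles from cycle 4 is one workable interval. At 21-day cycles it matches the imaging interval in 7.1.5.2, "Tumor Assessments of known sites of disease (every 9 weeks; 63 +/- 7 days", and its first point coincides with the research blood sample in 7.1.2.7, taken "after 3 cycles of treatment, and at treatment discontinuation or progression". Another fixed interval would also serve. Treatment and recording rules need no change.

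The cost is marks in two tables, one line of text, the assays counted above, and follow-up of some extra low-grade findings. CBC and chemistry are already drawn at every one of these visits, so there is no added visit or venepuncture.
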